- 15. Information on all medications and treatments received by the subject within the 4 weeks preceding the Screening visit through the final visit will be recorded in the CRF.

Assessment*	Administered to	Special Instructions
Vineland-II	Parent/Caregiver	Must be administered prior to the other developmental tests at Screening (ie, BSID- III, KABC-II, BOT-2, CCC-2) Administered in-person
BSID-III ¹	Subject	At Screening, administered to subjects with Vineland-II age equivalent of <3 years, 6 months) Administered in-person
KABC-II ¹	Subject	At Screening, administered to subjects with Vineland-II age equivalent of \geq 3 years, 6 months Administered in-person
BOT-2 Brief Form ²	Subject	Administered only to subjects who complete the KABC-II.
CCC-2 ²	Parent/Caregiver	Administered only to subjects completing the KABC-II.
ZBI, 12-item	Parent/Caregiver	
SF-10	Parent/Caregiver	
SBRS	Parent/Caregiver	
CSHQ	Parent/Caregiver	

14.5 Appendix E: NGLU-CL02 Neurocognitive, Developmental and QOL Assessments

* All neurocognitive, developmental and QOL assessments are administered during the Screening visit. Assessments can be performed over multiple days.

¹Either the BSID-III or KABC-II will be administered to the subject depending on the mean age equivalent determined by the Vineland-II at Screening. Refer to supplemental instructions provided to each site regarding when to switch the BSID-III or KABC-II.

²Administered only to subjects completing the KABC-II

3. LIST OF ABBREVIATIONS AND DEFINITIONS OF TERMS

The following abbreviations and acronyms are used in this SAP.

Table 1:Abbreviations and acronyms

Abbreviation or acronym	Explanation
ADA	Anti-drug antibodies
AE	Adverse event(s)
AESI	Adverse events of special interest
ATC	Anatomical therapeutic chemical
BBB	Blood brain barrier
BOT-2	Bruininks-Oseretsky Test of Motor Proficiency, Second Edition
BSID-III	Bayley Scales of Infant and Toddler Development, Third Edition
CCC-2	Children's Communication Checklist, Second Edition
CSF	Cerebrospinal fluid
CSF-AI	Cerebrospinal fluid/serum albumin index
CSHQ	Children's Sleep Habits Questionnaire
CSP	Clinical study protocol
CSR	Clinical study report
ECG	Electrocardiogram
eCRF	Electronic case report form
FAS	Full Analysis Set
FDNA	Facial Dysmorphology Novel Analysis
HGF	Hepatocyte growth factor
HS	Heparan sulfate
IAR	Infusion-associated reaction
ICH	International Conference on Harmonization
IgG	Immunoglobulin G
IMP	Investigational Medicinal Product
IV	Intravenous(ly)
KABC-II	Kaufman Assessment Battery for Children, Second Edition
MedDRA	Medical Dictionary for Regulatory Activities
MPS IIIB	Mucopolysaccharidosis III, type B
MRI	Magnetic resonance imaging
NAGLU	Alpha-N-acetylglucosaminidase
NRE	Non-reducing end
NVI	Non-verbal index
PD	Pharmacodynamic(s)
РК	Pharmacokinetic(s)
РТ	Preferred Term
QOW	Once every other week
Rel Day	Relative study day
SAE	Serious adverse event
SAP	Statistical analysis plan
SBRS	Sanfilippo Behavior Rating Scale
SD	Standard deviation
SDTM	Study Data Tabulation Model
SF-10	10-item Short Form Health Survey for Children
SI	International system of units
MRI	Magnetic resonance imaging
SOA	Schedule of Assessments
5011	Schedule 017155655hlott5

Abbreviation or acronym	Explanation
SOC	System Organ Class
TEAE	Treatment-emergent adverse event
TESAE	Treatment-emergent serious adverse event
US	United States (of America)
Vineland-II	Vineland Adaptive Behavior Scales, Second Edition
WHO	World Health Organization
WHO-DD	World Health Organization Drug Dictionary
ZBI	Zarit Burden Interview 12-item short form

4. **DESCRIPTION OF THE PROTOCOL**

Study NGLU-CL02, *A Phase I/II Open Label Study in MPS IIIB Subjects to Investigate the Safety, Pharmacokinetics, and Pharmacodynamics/Efficacy of SBC-103 Administered Intravenously,* is an open label, 3-part Phase I/II study designed to evaluate the safety, tolerability, pharmacokinetics, and pharmacodynamics/efficacy of intravenous (IV) administration of SBC-103 in subjects with mucopolysaccharidosis III, type B (MPS IIIB, Sanfilippo B) with evaluable signs or symptoms of developmental delay.

Study NGLU-CL02 is conducted in 3 parts: Part A (Initial therapy at 0.3, 1, or 3 mg/kg), Part B (Extended Therapy at 1 and/or 3 mg/kg), and Part C (Extended Therapy at 5 and/or 10 mg/kg).

Part A is designed to assess the safety, tolerability, pharmacokinetics (PK), and pharmacodynamics (PD)/efficacy of 3 escalating doses of SBC-103 dosed once every other week (QOW) over 24 weeks.

Part B is designed to assess the safety, tolerability, PK, and PD/efficacy of chronic dosing for an extended period of time and to allow for intra-subject dose modification based on available data.

Following Part A and prior to entering Part B, subjects will have a 4-week period of time off therapy (instead of the usual 2 weeks between doses that occurs with QOW dosing) in order to assess the impact of treatment interruption on safety, tolerability, and select PD/efficacy markers, including the assessment of reversibility of any observed on-therapy changes in heparan sulfate (HS).

Part C (added with Amendment 6 and based on preliminary safety and PK/PD data from Parts A and B) is designed to assess the safety, tolerability, PK, and PD/efficacy of SBC-103 at 5 and 10 mg/kg QOW, as well as to assess the effects on chronic dosing. Subjects will be followed on Part C until the end of the treatment period at 156 weeks (a period of between 90 and 110 weeks). Intra-subject dose modification is permitted in Part C (based on data review and Sponsor agreement) with the intent to treat subjects with the lowest potentially efficacious dose that is safe and tolerable.

The protocol can be referenced for additional details. The Part C Schedule of Assessments (SOA) is attached in Appendix 9.1.4 of this Statistical Analysis Plan (SAP).

On 11 Jul 2017, Alexion decided to stop the clinical development program with SBC-103. A clinical study report (CSR) will detail the final demographic, disposition, exposure, and safety data of each study.

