1.4 Clinical Data

1.4.1 Data for SBC-103

As this is a first-in-human study, no clinical data for SBC-103 were available when this study was planned and initiated.

As described in Section 3.1, subjects in Part A receive IV infusions of SBC-103 at 1 of 3 doses (0.3, 1, or 3 mg/kg) QOW for 24 weeks followed by a 4-week temporary interruption of therapy prior to re-initiating therapy at Week 28 in Part B. Modifications to dose or dosing frequency for individual subject(s) is permitted in Part B with the intent of treating subjects with the lowest potentially efficacious dose that is safe and tolerable.

As of 20 November 2015, preliminary data were available for all subjects enrolled in this study, including approximately 20 to 40 weeks (~11 to 20 QOW doses) of preliminary safety data, and preliminary PK and PD data through Week 12 (~7 QOW doses).

These data are briefly summarized below. *However, it should be noted that these are preliminary data from an ongoing study and an open database, and therefore, are subject to change based on data review, reconciliation, and/or auditing.*

As described in Section 3.1.1, approximately 9 subjects were to be enrolled in this study across 3 dose cohorts (n=3/cohort) with a provision to permit enrollment of additional subjects if more than 3 subjects in a cohort had entered Screening and were eligible to participate in the study. A total of 11 subjects were sequentially enrolled in this study into Cohort 1 (0.3 mg/kg, n=3), Cohort 2 (1 mg/kg, n=4), or Cohort 3 (3 mg/kg, n=4). All subjects had a confirmed diagnosis of MPS IIIB and documented developmental delay with onset before 6 years of age. The majority of subjects enrolled in this study are PPD and the mean (SD) age was 7.5 (2.82) years for subjects in the 0.3 mg/kg dose cohort, 6.6 (4.54) years for subjects in the 1 mg/kg dose cohort, and 4.5 (2.10) years for subjects in the 3 mg/kg dose cohort.

Page 28 of 121

As of 20 November 2015, all 3 subjects in Cohort 1 have completed Part A of the study and have received between 5 and 7 doses of SBC-103 at 1.0 mg/kg QOW in Part B; all 4 subjects in Cohort 2 have completed Part A and 2 of these subjects have received 2 doses at 3.0 mg/kg QOW in Part B; and the 4 subjects in Cohort 3 have completed between 20 and 24 weeks of Part A at 3.0 mg/kg.

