3.1.3 Part C (Therapy at 5 and/or 10 mg/kg)

Subjects who meet eligibility criteria for Part C (see Section 4.3.4) may begin Part C at their next scheduled visit provided that regulatory and ethics committee review and approval (where required) have been obtained for at their study site and the criteria for dosing in Section 3.1.3.1 are met. Part C is a randomized, open-label assessment of SBC-103 at doses of 5 or 10 mg/kg administered IV. Subjects will be randomized such that at least 1 subject from each cohort assigned in Part A will receive SBC-103 at 5 mg/kg and at least 1 subject from each cohort assigned in Part A will receive SBC-103 at 10 mg/kg. Thus each of the assigned dose levels from Part A will be represented in each of the 2 dose levels being studied in Part C. Treatment in Part C will continue through Week 156 of the study.

Details regarding the maximum planned dose, dose adjustments, and stopping rules in the event of poor tolerability are provided in Section 6.1 and Section 6.2.

Safety, PK and PD/efficacy assessments will be performed in all subjects as noted in the SOA for Part C, detailed in Section 14.4 (Appendix D). To minimize unnecessary risk and burden to subjects, the following study assessments in Part B may be used as baseline assessments for Part C in lieu of repeating the assessment prior to the first dose in Part C:

- An MRI performed within 8 weeks prior to Day 0 in Part C (Day 0C) may be used as the baseline assessment for Part C in lieu of performing an MRI on Day 0C.
- Neurocognition testing performed within 8 weeks prior to Day 0C may be used as the baseline assessment for Part C in lieu of performing neurocognition testing on Day 0C.
- A lumbar puncture performed within 4 weeks prior to Day 0C may be used as the baseline assessment for Part C in lieu of performing a lumbar puncture on Day 0C.

In addition, because individual subjects may reach Week 156 of the study at unique study visits in Part C, the following assessments in Part C may be used as the end-of-treatment assessment in lieu of repeating the assessment at Study Week 156:

- An MRI performed within 8 weeks prior to Study Week 156 may be used as the final assessment for Part C in lieu of performing an MRI at Study Week 156.
- Neurocognition testing performed within 8 weeks prior to Study Week 156 may be used as the final assessment for Part C in lieu of performing neurocognition testing at Study Week 156.

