8 STATISTICAL PLAN

8.1 General Considerations

Descriptive summary statistics will be provided for demographics, disposition and dose exposure. Number and percentage of subjects who discontinued from the study, along with reasons for discontinuations will be tabulated and described in listings.

Continuous data will be summarized using descriptive statistics (number of subjects, mean, standard deviation, median, minimum, and maximum) and, where appropriate, graphic representation and two-sided 95% confidence intervals (CI); categorical data will be summarized by sample size, proportions, and two-sided 95% CIs.

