4.1.4. Assessments / Parameters Included in Analysis

- Demographics
- Disposition
- Use of Prior and Concomitant Medications (Listing only)
- Treatment Exposure, Dosing Administration and Infusion Summary (Listings only)
- Treatment Emergent Adverse Events (TEAEs)
- Treatment Emergent Serious Adverse Events (TESAEs)
- Infusion Associated Reactions (IAR)
- Anti-drug Antibody (ADA) Assay and Titer Results
- Laboratory Parameters: Hematology, Chemistry, Urinalysis, including Coagulation, Renal Function, and Liver Function (Listings only).
- Lumbar Puncture: CSF Findings and CSF-AI Ratio (listings only)
- Vital Signs (listing only)

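### Exposure is cut to by-patient listings, so the adverse-event results by Part C dose carry no summary of time or infusions, and the planned 90–110 weeks is left unqualified beside the programme stop

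*SAP*

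**What the plan says.** Protocol 8.1 commits to an exposure summary: "Descriptive summary statistics will be provided for demographics, disposition and dose exposure". SAP 4 says the study report will detail exposure, and SAP 4.1 names exposure among the data kept for summaries and listings. The controlling list in SAP 4.1.4 then reads "Treatment Exposure, Dosing Administration and Infusion Summary (Listings only", and SAP 7.3.1 specifies only listings by patient, Part C dose assignment and visit.

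Adverse events are summarised as numbers of events and as numbers and percentages of patients, by Part C dose assignment and overall, once for the whole study and once for Part C (SAP 7.3.2). The denominator is the number of treated patients (SAP 7.3.2.2): 5 children assigned to 5 mg/kg and 6 to 10 mg/kg (SAP 9.3.2).

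On duration, Protocol 3.1.3 says "Treatment in Part C will continue through Week 156 of the study". SAP 4 says children will be followed "until the end of the treatment period at 156 weeks (a period of between 90 and 110 weeks". Later in the same section it records that on 11 July 2017 the sponsor "decided to stop the clinical development program with SBC-103". The SAP is dated 1 September 2017 and gives no other Part C duration.

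**The concern.** A percentage of patients with an event can be interpreted only if the reader knows how long, and how often, those patients were exposed. Four features of this study make exposure uneven:

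- Children enter Part C at different times (SAP 9.4.1).
- Dose changes are allowed within Part C (SAP 4).
- Treatment-emergent events are counted from the first dose in Part A. The whole-study results shown under 5 or 10 mg/kg therefore include time at 0.3–3 mg/kg.
- The programme was stopped on a calendar date.

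The rule for infusion-associated reactions adds to this. A patient may be counted again for reactions on a further dosing day (SAP 7.3.2.5.2), so that count can rise with the number of infusions, which is never summarised.

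The only Part C duration a reader finds in the SAP is the planned one. If it passes unqualified into the study report, it could be taken as the length of safety observation at the two highest doses.

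**Working it through.** **1. The plan's own figure.** Part C duration = 156 − study week at Part C entry.
- 156 − 110 = Week 46 and 156 − 90 = Week 66.
- Entry at Weeks 46–66 agrees with SAP 9.4.1, where entry falls before, at or after Week 52. The figure is coherent as a plan. It cannot be rebuilt independently, because entry weeks are not given.

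**2. Where the children were on 20 November 2015 (Protocol 1.4.1).** All 11 had "approximately 20 to 40 weeks (~11 to 20 QOW doses) of preliminary safety data".
- Cohort 1 children "have received between 5 and 7 doses of SBC-103 at 1.0 mg/kg QOW in Part B". Part B starts at Week 28, so a seventh two-weekly dose falls at 28 + 6 × 2 = Week 40. The most advanced child was between Week 40 and just under Week 42.
- Cohort 2 had finished Part A, and two of its children had received two doses at 3 mg/kg in Part B.
- Cohort 3 had completed 20–24 weeks of Part A.
- Nobody was in Part C.

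**3. Elapsed time.**
- To the stop: 599 days / 7 = 85.6 weeks.
- To the SAP date: 651 days / 7 = 93.0 weeks.

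**4. Could anyone have reached Week 156?** Required study week on 20 November 2015 = 156 − elapsed weeks.
- For the stop: 156 − 85.6 = 70.4. For the SAP date: 156 − 93.0 = 63.0. The maximum was about 40–42, so the answer is no on both dates.
- Study weeks at the stop: 20 + 85.6 = 105.6 up to 42 + 85.6 = 127.6, which is 28.4–50.4 weeks short.
- Study weeks at the SAP date: 113.0 to 135.0, which is 21.0–43.0 weeks short.

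**5. Ceiling on Part C time.** With nobody in Part C on 20 November 2015, Part C time cannot exceed the elapsed time.
- At the stop: at most 85.6 weeks, so the lower planned figure of 90 was out of reach by at least 4.4 weeks.
- At the SAP date: at most 93.0 weeks. Excluding 90 here requires a Part C start after 11 December 2015 (90 weeks before 1 September 2017).

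**6. How uneven exposure could be (illustration only).** Assume entry at the implied Weeks 46–66, study weeks of 20–40 on 20 November 2015, and uninterrupted two-weekly dosing up to the stop.
- Shortest: 105.6 − 66 = 39.6 Part C weeks, about 20 infusions (19 full two-week intervals + 1).
- Longest: 125.6 − 46 = 79.6 Part C weeks, about 40 infusions (39 + 1).

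Under those assumptions one child could have twice the infusions of another. With 5 and 6 children, a single child moves a percentage by 1/5 = 20 or 1/6 = 16.7 points. No planned table would show which exposure lies behind it.

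**The case against.** The strongest reply has three parts.

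First, 90–110 weeks is not an error. It stands in a section describing the protocol, is in the future tense, is arithmetically coherent, and feeds no analysis. That stands. A reader might infer that the SAP claims safety was observed for 90–110 weeks, or might divide the planned duration by a guessed actual one to get an overstatement factor. The documents support neither. The SAP never says the time was observed, and a factor would need last-dose and entry dates that are not given. The 11 July 2017 date marks a decision about the programme, not a last infusion, and SAP 7.2.1.3 still describes the centres as participating.

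Second, the move to listings is disclosed. SAP 4.1 announces a reduced set of analyses, and with 11 children a reader could count infusions from listings that give every start and stop time. This too is fair, but it does not settle the matter. Exposure was kept in the reduced scope and SAP 4.1 names it for summaries. No reason is given for dropping the summary of the quantity needed to read the retained safety tables.

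Third, no inferential comparison of doses is planned, and rates from 5 and 6 children will be imprecise. Both are true. Even so, results set side by side by dose need an exposure context when they are purely descriptive.

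**Conclusion.** The point holds in two parts.

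The main part is the missing exposure summary. Protocol 8.1 promises it, the SAP plans none, and the study's only remaining objective depends on it. This rests on the text alone and does not depend on when dosing ended.

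The lesser part is the unqualified planned duration. At the stop no child could have had more than 85.6 Part C weeks, and no child could have been at Week 156 at the stop or at the SAP date. This rests on the approximate, preliminary status given in Protocol 1.4.1; the Week 156 margin, at least 21 weeks, is wide enough to absorb that.

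Two further readings go beyond the documents:

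- A reader might infer that 90 Part C weeks was also impossible at the SAP date. That is likely: entry no earlier than the implied Week 46 puts the most advanced child at 89.0 weeks at most, and the protocol of 21 January 2016 still describes Part C prospectively. But it relies on an inferred start after 11 December 2015, and the bare ceiling is 93.0 weeks.
- A reader might infer that the 10 mg/kg group had less time, because its first dose waits for two doses in one child at 5 mg/kg and a safety committee review (Protocol 3.1.3.1). That delays only the first 10 mg/kg child relative to the first 5 mg/kg child. The other children enter as they become eligible and their sites are approved, so the order of the groups is not known.

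**What to change.** - **SAP 7.3.1:** add one table, by Part C dose assignment and overall, giving weeks from first to last dose and number of infusions received, with infusions split by dose actually received. Show it for Part C and for the whole study.
- **SAP 7.3.2 and 7.3.2.5.2:** beside n (%), show treatment-emergent adverse events per patient-year and infusion-associated reactions per infusion.
- **SAP 4:** label 90–110 weeks as the Part C duration planned before the stop, and report the actual duration in the study report from the new table.

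No separate table of sponsor termination is needed. SAP 7.1.1 already tabulates reasons for discontinuation, and Protocol 4.5.1 lists termination by the sponsor among them.

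The cost is one table and two columns, built from dosing data already being listed. The rates will be imprecise with 5 and 6 children and should be presented as descriptive.

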4.1. Changes from Analyses Specified in the Protocol

The data analyses, data summaries and data presentations specified for the NGLU-CL02 CSR represent a reduced subset of the overall total data analyses, data summaries, and data presentations described in the NGLU-CL02 final approved Clinical Study Protocol (CSP) version (Amendment 7, 21 January 2016) for the full study. Only demographic, disposition, safety and exposure data will be used to create data summaries and listings for the reduced subset of the CSP specified full study parameters presented by Part C dose assignment (5 or 10 mg/kg

QOW) and overall (5 and 10 mg/kg QOW combined). Only the assessments/parameters specified in Section 4.1.4 will be included.

4.1.1. Primary Objective

The primary objective of this CSR SAP is to evaluate the safety and tolerability of IV administration of SBC-103 in subjects with mucopolysaccharidosis III, type B (MPS IIIB, Sanfilippo B) with evaluable signs and symptoms.

4.1.2. Secondary Objectives

No secondary objectives will be addressed in this SAP.

4.1.3. Exploratory Objectives

No exploratory objectives will be addressed in this SAP.

4.1.4. Assessments / Parameters Included in Analysis

- Demographics
- Disposition
- Use of Prior and Concomitant Medications (Listing only)
- Treatment Exposure, Dosing Administration and Infusion Summary (Listings only)
- Treatment Emergent Adverse Events (TEAEs)
- Treatment Emergent Serious Adverse Events (TESAEs)
- Infusion Associated Reactions (IAR)
- Anti-drug Antibody (ADA) Assay and Titer Results
- Laboratory Parameters: Hematology, Chemistry, Urinalysis, including Coagulation, Renal Function, and Liver Function (Listings only).
- Lumbar Puncture: CSF Findings and CSF-AI Ratio (listings only)
- Vital Signs (listing only)

4.2. Changes from Analyses Specified in the Previous Version of the SAP

Not applicable.

5. **DEFINITIONS**

5.1. Efficacy

5.1.1. **Primary Endpoint(s)**

The primary objective is to evaluate the safety and tolerability of IV administration of SBC-103, and as such, there is no primary efficacy endpoint.

5.1.2. Secondary Endpoints

Analyses of secondary efficacy endpoints will not be included in the CSR.

5.1.2.1. Pharmacokinetic (PK) Parameters

Analyses of PK data will not be included in the CSR.

5.1.2.2. Pharmacodynamic (PD) Parameters

Analyses of PD or PK/PD data, including HS, will not be included in the CSR.

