1.5 Dose Rationale and Risk/Benefits

1.5.1 Study Dose Rationale

1.5.1.1 Defining a Pharmacologically Active Dose

Extended treatment with an ERT is generally required to offer any benefit for a chronic disease such as MPS IIIB, and in a pediatric population such as this, it is important to provide some prospect for benefit with the investigational treatment. Therefore, this study was designed to support chronic dosing for an extended period of time and to allow for intra-patient dose escalation based on evidence of biological activity. Because of the profound neurocognitive abnormalities that dominate the clinical presentation of patients with MPS IIIB, HS reduction in CSF is considered to be an important predictor of potential clinical efficacy in these patients, and therefore, an important PD endpoint representative of biological activity.

However, there is no precedence in MPS IIIB for the magnitude of reduction of HS in the CNS that will be required for efficacy. Based on a combination of data including: the size of systemic substrate reduction with other IV enzyme replacement therapies in MPS I (Clarke 2009, *Pediatrics*) and MPS II (Muenzer 2006, *Genet Med*), reduction of CSF substrate from intrathecally (IT) administered ERT in a related disease, MPS IIIA (Breen 2013, *www.ashg.org*), and the degree of reduction of HS in the brain in the NAGLU mouse model experiments (SBC-103 IB), an estimated substrate reduction of ~40% in the CSF in humans is considered to be a reasonable target to identify a pharmacologically active and potentially efficacious clinical dose of SBC-103.

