1.5.1.4 Part C (Therapy at 5 and/or 10 mg/kg): Dose Selection Rationale

Preliminary PD data through Week 12 showed that while decreases in heparan sulfate in CSF were moderately correlated with increased serum PK exposure (AUC_{last} and C_{max}), the maximum HS reduction in CSF across all 3 doses was 16.5%, which did not reach the target reduction of ~40% (see Section 1.5.1.1). Greater systemic reduction in substrate was observed following administration of SBC-103; the maximum HS reduction in serum observed across all 3 doses was 68.8%, which is consistent with systemic reductions observed for other ERTs. In addition, the initial safety profile of SBC-103 indicates that it appears to be safe and well tolerated in patients with MPS IIIB (see Section 1.4.1.1).

In the NAGLU-deficient mouse model, SBC-103 administered QW as IV bolus doses of 0.3, 1, 3, 5, or 10 mg/kg for 4 weeks resulted in decreases in HS in the liver and brain, and while near maximal HS decreases were observed in the liver at doses \geq 1 mg/kg, HS levels in the brain continued to decrease with each increasing dose (SBC103-P010). Furthermore, similar reductions in HS (brain and liver) were observed in the NAGLU-deficient mouse model regardless of administration regimen (ie, IV bolus QW, IV bolus QOW, or IV infusion QOW)

ALEXION PHARMACEUTICALS, INC. PROPRIETARY AND CONFIDENTIAL: DO NOT COPY OR DISTRIBUTE WITHOUT PERMISSION FROM ALEXION

(SBC103-P010; SBC103-P013). Therefore, it is reasonable to expect that greater reductions of HS in CSF may be expected at increased dose levels in this clinical study. Dose escalation above 3 mg/kg in Part C will explore whether substrate reduction in the CNS can be increased with higher doses (5 and 10 mg/kg) or whether maximal clearance from the CNS has been achieved, thus allowing for identification of doses for extended therapy in this study and for future clinical development that will ensure the greatest potential for clinical benefit.

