7.2.2.4.2. Pharmacodynamic Analyses

Analyses of pharmacodynamic (PD) data will not be included in the CSR.

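### The planned CSR contains no heparan sulfate output, so it cannot report whether 5 and 10 mg/kg increased the reduction in CSF

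*SAP*

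**What the plan says.** **Protocol.** Section 1.5.1.1 sets a benchmark for a pharmacologically active dose: "an estimated substrate reduction of ~40% in the CSF in humans is considered to be a reasonable target". Section 1.5.1.4 reports that the largest CSF HS reduction through Week 12 was 16.5%, short of that benchmark, and that the largest serum reduction was 68.8%. It then gives the purpose of the new doses: "Dose escalation above 3 mg/kg in Part C will explore whether substrate reduction in the CNS can be increased with higher doses", or whether clearance from the CNS is already maximal. HS change in CSF, serum and urine is a secondary objective (2.2) and endpoint (3.4.2). Section 8.6 commits to PD analyses for Parts A and C and/or the whole study, to listings of total HS, and to summaries of observed values and changes or percent changes from baseline at each time point, overall and by regimen.

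**SAP.** Section 4 records the context: "On 11 Jul 2017, Alexion decided to stop the clinical development program with SBC-103". Section 4.1 restricts the output: "Only demographic, disposition, safety and exposure data will be used to create data summaries and listings". Section 4.1.2 adds: "No secondary objectives will be addressed in this SAP". Section 5.1.2.2 states: "Analyses of PD or PK/PD data, including HS, will not be included in the CSR", and 7.2.2.4.2 repeats: "Analyses of pharmacodynamic (PD) data will not be included in the CSR". The permitted outputs in 4.1.4 include listings of routine CSF findings and the CSF/serum albumin index (CSF-AI), but nothing on HS.

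**The concern.** HS in CSF is the measurement on which the protocol rests the move above 3 mg/kg. Protocol 1.5.2.1 says a lumbar puncture is needed to find out whether the drug lowers HS in the CNS. A final report without HS leaves that question unanswered in the one document both plans provide for.

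The timing adds to the concern. The study is open label (Protocol 6.7). Safety and PD data from Part C were to be reviewed on an ongoing basis to guide dose selection (3.3.3), and the sponsor was to review PD/efficacy every 6 months in the first year and at least annually after that (7.5). A decision on what to report, taken once results can be seen, may depend on those results. Disclosing the decision makes it transparent but does not supply the missing result.

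**Working it through.** **1. Is any HS output left?** SAP 4.1 limits both summaries and listings to demographic, disposition, safety and exposure data and admits only the items in 4.1.4. HS is not among them. Planned HS tables: 0. Planned HS listings: 0. Protocol 8.6 promised both listings and summaries.

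**2. Does a safety-only scope explain what was kept?** In part. Routine CSF findings belong to the primary safety endpoint (Protocol 3.4.1). CSF-AI does not: it is an exploratory biomarker (3.4.3), and SAP 4.1.3 says no exploratory objective is addressed. Yet CSF-AI is listed, while HS from the same punctures, a secondary endpoint that Protocol 5.2.1.4 prioritises when CSF is short, is not.

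**3. Were Part C samples due before the stop?**
- 11 Jul 2017 to 01 Sep 2017 = 52 days from stop decision to SAP.
- At 20 Nov 2015 children were about 20 to 40 weeks into the study (Protocol 1.4.1). From then to 11 Jul 2017 is 599 days / 7 = 85.6 weeks, so they were at about study Week 105.6 to 125.6 at the stop.
- SAP Section 4 gives 90 to 110 weeks of Part C up to Week 156, so entry was at about Week 156 − 110 = 46 to 156 − 90 = 66.
- Time in Part C at the stop: at least 105.6 − 66 = 39.6 weeks, at most 125.6 − 46 = 79.6 weeks.

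Day 0C, Week 12C and Week 24C were therefore due for every child. Week 40C was borderline for the latest entrant, and Week 52C was not due for all.

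**4. How many punctures?** From the schedules in Protocol Appendices A, B and D:
- Part A: Day 0, Weeks 12 and 24 = 3.
- Part B before the earliest Part C entry: Weeks 28 and 40 = 2.
- Part C: Day 0C, 12C, 24C = 3, and with 40C and 52C = 5.

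Through Week 24C: 8 × 11 = 88. Through Week 52C: 10 × 11 = 110. The 110 is a scheduled maximum for children who entered Part C by Week 52, with no dropout and no earlier puncture standing in for Day 0C. A child who entered later would also have had the Week 52 puncture of Part B.

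**5. Would so few children tell us anything?** Part C has 5 children at 5 mg/kg and 6 at 10 mg/kg. The half-width of a 95% interval for mean percent change is t(0.975, n−1) × SD / √n, which is 1.24 SD (n = 5), 1.05 SD (n = 6) and 0.67 SD (n = 11). The documents give no SD; I assume 10 to 30 percentage points.

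| SD (points) | n = 5 | n = 6 | n = 11 |
|---|---|---|---|
| 10 | ±12.4 | ±10.5 | ±6.7 |
| 15 | ±18.6 | ±15.7 | ±10.1 |
| 20 | ±24.8 | ±21.0 | ±13.4 |
| 30 | ±37.2 | ±31.5 | ±20.2 |

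The distance from 16.5% to 40% is 23.5 points. The half-width is below that if the SD is under about 18.9 (n = 5), 22.4 (n = 6) or 35.0 (n = 11). This gauges readability only; no test is proposed.

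**6. Why the baseline matters.** Part C baseline is on treatment. As an illustration, a child already 16.5% down at Part C entry stands at 0.835 of the untreated value. A total reduction of 40% then needs 1 − 0.60/0.835 = 28.1% from Part C baseline, whereas 40% from Part C baseline would be 1 − 0.835 × 0.60 = 49.9% from untreated. The two percent changes answer different questions and should both be shown.

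**The case against.** The strongest defence is that HS was not singled out. The SAP also drops PK, neurocognition, MRI, ECG, disease characteristics, protocol deviations and every other secondary and exploratory analysis. It says so openly under changes from the protocol, and it keeps the primary objective, safety. A uniform cut to an abbreviated report after a programme stops is ordinary practice. This stands, and it weighs against reading the omission as aimed at HS.

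Three stronger readings are tempting, and the documents do not support them.

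- A reader might infer that HS was dropped because Part C results were poor. The documents show no Part C HS result and no motive. They show only that reviews of PD data were planned.
- A reader might infer that Part C was a test of reaching 40%. The stated question is whether CNS substrate reduction can be increased or is already maximal. The 40% is an estimated benchmark, set where Protocol 1.5.1.1 says there is no precedent, with no responder definition or decision rule attached.
- A reader might infer that the HS data are lost to later programmes. The SAP governs the CSR only. Protocol 8.7 provides for interim summaries to regulators or the scientific community, and Section 12 intends publication. Neither document, however, specifies another final HS analysis.

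The small sample is a fair caution but no reason for omission: a listing needs no precision, and Protocol 8.6 planned descriptive summaries at this size.

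**Conclusion.** The point holds as the disclosed loss of a planned result. The CSR will carry no HS table or listing, against a protocol commitment to both, and so cannot report whether 5 and 10 mg/kg increased the reduction in CSF HS. Selective reporting is not shown. Result-dependent omission cannot be excluded either, because the study is open label, PD review was planned during Part C, and the SAP (which records no earlier version) postdates the stop. The SAP gives no specific reason for dropping HS; the stop decision is the only context.

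The primary safety conclusions are unaffected, and HS is one of several unranked secondary endpoints. The 88 and 110 punctures describe scheduled participant burden, not the size of any bias, and the same punctures also supply the CSF findings that are still listed. The timeline assumes visits on schedule and no dropout; the precision figures rest on the assumed SD range.

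**What to change.** Add to SAP 4.1.4, and amend 5.1.2.2 and 7.2.2.4.2 to match:

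- A by-patient listing of total HS in CSF, serum and urine by visit, with percent change from Part A baseline and from Part C baseline, 100 × (value − baseline) / baseline, using the baseline definitions already in SAP 9.4.1.
- The descriptive summary promised in Protocol 8.6: observed values and percent change by visit, by Part C dose assignment and overall, with no inference.

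If the 40% benchmark is shown at all, present it only as a reference against change from the untreated Part A baseline, and label it post hoc. A count of children passing 40% appears in no planned analysis, and adding one now would itself be a choice made after open-label data.

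The cost is one listing and one small table, with the programming and quality control that go with them, in a report meant to be short. Baselines and the rule for substituting a lumbar puncture are already specified, and other lumbar-puncture listings are already planned.
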